## 9 Statistical Methodology

A separate document entitled “Statistical Analysis Plan” (SAP) will describe further details about the analyses to be conducted in this study. An overview of the general statistical methods is provided in the following sections.

### 9.1 Analysis Timing and Blinding Considerations

Consistent with the study design, the primary time point for analysis is Month 5. The primary analysis for this study will be performed after the last subject has completed the Month 5 study visit, at which time the study database will be locked and the treatment allocation codes unblinded for analysis. This analysis will form the primary basis for the assessment of the study objectives.

Continuing data collection through the long-term follow-up will be performed through Month 24. While Investigators and subjects will remain blinded to the treatment allocations, assessment and analysis of outcomes will be performed by the Sponsor in an on-going manner, to better understand the longer-term effects (on both safety and efficacy) of the therapy.

### 9.2 Sample Size Determination

The primary objective of this study is to assess the safety and tolerability of AVT001, as compared to placebo, in subjects with type 1 diabetes. A sample size of 14 subjects treated with AVT001 will provide at least 80% power to observe at least one occurrence of treatment-emergent adverse events with a true underlying incidence of 12%. The sample size provides the same power to detect at least one occurrence of local tolerability events relating to the i.v. administration of study drug.

Secondary objectives of this study include assessment of changes in pharmacodynamic markers, including (increases) in the CD8+ T-cell reg system, C-peptide levels, and HbA1c. The sample size of 14 subjects treated with AVT001 and 7 subjects treated with placebo will provide estimates of the mean and standard deviation of the treatment benefit of AVT001 as compared to placebo in these endpoints.

To account for an estimated 10% potential dropout prior to the completion of the Month 5 safety/efficacy assessment post-first dose, a total sample size of approximately 24 subjects will be randomized, in a 2:1 ratio of AVT001:Placebo.

### 9.3 Analysis Populations

There are two analysis populations defined for this study.

- The Safety population is defined as all subjects who receive at least one dose of study medication. Safety outcomes will be assessed using the Safety population.
- Pharmacodynamic outcomes will be assessed in subjects with at least one post-baseline assessment for the evaluation of the CD8+ T-cell reg system biomarker.

Other analysis populations may be defined in the SAP.

### 9.4 Baseline characteristics, Patient Disposition and Medication

Key baseline characteristics will be tabulated by treatment group. Patient disposition will be described, including patient completion status and reasons for premature discontinuation from the study. Prior and concomitant medications will be tabulated (with a focus on new-onset medications, ie, those that are started after study treatment has commenced).

### 9.5 Adverse Events

Adverse events will be reported using the MedDRA coding dictionary. Tabulations will include an overall incidence of at least one adverse event, incidence within body system, and incidence by preferred term. Each subject may only contribute once (ie, first occurrence) to each of the incidence rates, regardless of the number of occurrences. The incidence of adverse events will be presented as follows:

- The incidence of treatment-emergent adverse events (TEAEs), ie, those events that start on or after the first dose of study medication, will be tabulated by treatment for the Treatment Phase. This will include events starting within 30 days following the last dose.
- The incidence of post-treatment events (those events that start more than 30 days following the last dose) will be tabulated.

Subjects with serious adverse events (including deaths) and subjects who discontinue due to adverse events will be listed. Subjects who have other significant serious adverse events deemed to be of special interest because of clinical importance will also be listed.

## 9.6 Severe Hypoglycemic Events and Insulin Log

The number and subject incidence of severe hypoglycemic events (defined in Section 11.1.7) will be tabulated by subject incidence (number and percent of subjects) as well as frequency (number of events per subject).

The total daily dose of insulin will be tabulated by visit from the insulin logs. Daily insulin usage will be listed from these logs.

## 9.7 Clinical Laboratories, ECGs, and Vital Signs

Descriptive statistics at Baseline, on-treatment, and change from Baseline will be calculated for the subjects who have both Baseline and on-treatment evaluations. Shifts from Baseline to on-treatment will be examined. Potentially clinically significant laboratory values will be identified and listed.

## 9.8 Pharmacodynamic Outcomes

Changes over time in CD8+ T-cell reg system, C-peptide levels, HbA1c, and antibody values will be assessed. For purposes of data presentation, where appropriate, a mixed model for repeated measures (MMRM) will be used to present changes in these parameters over time. Details regarding this MMRM will be provided in the SAP.

### 9.8.1 CD8+ T-cell reg system

A “potency assay” has been established to measure the specific suppression (inhibition) of the CD8+ regulatory T-cells to the target cells as one parameter to evaluate the efficacy of the AVT001 treatment. The data of maximum suppression of CD8+ regulatory T-cells from treated T1D subjects before the treatment versus after the treatment, with healthy people as a system control, determines whether there is a regained suppressive function of the CD8+ regulatory T-cells following the AVT001 treatment. Such values might suggest the effectiveness of treatment. Analyses for these outcomes will be specified in the SAP.

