### 5.2 Secondary Outcomes

- To determine whether, among T1D subjects with *in vitro*-reversible defects in the CD8+ T cell regulatory system, infusion of AVT001 will lead to an *in vivo* reconstitution of this system.
- To determine whether, among T1D subjects with *in vitro*-reversible defects in the CD8+ T cell regulatory system, infusion of AVT001 will result in amelioration of  $\beta$  cell destruction as defined by preservation of stimulated C-peptide.

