## 6 Subject Selection and Withdrawal

### 6.1 Inclusion Criteria

Subjects who meet *all* of the following criteria are eligible for enrollment as study participants:

1. Diagnosis of type 1 diabetes, within 12 months of first dosing, confirmed by positive lab result for one or more of the following types of autoantibodies:
  - a. Glutamic acid decarboxylase (GAD65)
  - b. Insulinoma associated protein 2 (IA-2, also known as ICA-512)
  - c. Zinc transporter 8 (ZnT8).
2. Age 16 or older and able to provide informed consent/assent.
3. Has a CD8+ T cell defect that is correctable *in vitro* by co-culture with immature dendritic cells loaded with the synthetic oligopeptide from Hsp60sp.
4. If a participant is female with reproductive potential, willing to avoid pregnancy through the duration of the trial.
5. Signed and dated written informed consent/assent.

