### **Screening Lab eligibility requirements**

- Potency Assay results from Screening do not expire.
- Auto-antibody and Viral testing results from Screening expire 6 months from collection.
- All other safety labs results from Screening expire after 90 days from collection including urine pregnancy tests for women of child bearing potential.

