## ALGORITHM FOR POTENCY ASSAY

As specified in the inclusion criteria 3 in the protocol, a subject is eligible for enrollment as the study participant, only if the subject “has a CD8+ T cell defect that is correctable in vitro by co-culture with immature dendritic cells loaded with the synthetic oligopeptide from Hsp60sp”.

Therefore, for the potency assay result of each patient on Visit 3/Day 1 (before the study treatment), should be imputed as the same as the corresponding potency assay result on Visit 1/Screening.

For potency assay results that are missing on any visits other than Visit 3/Day 1, no imputation will be performed.

---

Author: [name]

Version Number: 2.0

Template No.: CS\_TP\_BS016 Revision 6

Version Date: 23Nov2022

Effective Date: 02Dec2019

Reference: CS\_WI\_BS005

---

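### Regained CD8+ suppressive function is judged by an uncontrolled before-versus-after comparison that starts from the selecting screening value, and no AVT001-versus-placebo potency analysis is specified

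*Combined protocol and SAP*

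**What the plan says.** Protocol Amendment 3, section 5.2, makes the first secondary question whether "infusion of AVT001 will lead to an *in vivo* reconstitution of this system". Section 9.8.1 is the only current text that says how the potency assay answers it: "The data of maximum suppression of CD8+ regulatory T-cells from treated T1D subjects before the treatment versus after the treatment", read against healthy people as an assay control, "determines whether there is a regained suppressive function of the CD8+ regulatory T-cells following the AVT001 treatment". It then adds "Such values might suggest the effectiveness of treatment" and leaves the analyses to the SAP. It names no threshold, test, visit or placebo comparison.

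The pre-treatment value is fixed by four other places:

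- Inclusion criterion 3 (section 6.1) admits a subject who "Has a CD8+ T cell defect that is correctable" in vitro.
- The screening laboratory rules in section 8.2.1 state "Potency Assay results from Screening do not expire", while the other safety laboratory results lapse after 90 days.
- In Table 3 the only potency entry on patient blood before dosing is at screening. The Visit 2 entry is for the manufactured product.
- SAP v2.0's summary of changes confirms that no Day 1 assay was planned. Its Appendix 1 says that the Day 1 value "should be imputed as the same as the corresponding potency assay result on Visit 1/Screening".

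On the comparison with placebo, protocol section 9.2 says that 14 AVT001 and 7 placebo subjects will allow the benefit over placebo to be estimated for endpoints that include the CD8+ system. Section 9.8 mentions an MMRM for presentation, with details left to the SAP. SAP v2.0 lists the potency assay as a secondary endpoint (section 2.2), omits it from the secondary endpoints that it analyses (16.2), and uses it as a covariate in models for other endpoints (16.2.2). Section 3.3 provides for a listing and for an internal evaluation by the sponsor, reported separately.

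**The concern.** In a randomised, placebo-controlled trial, the stated criterion for the mechanism endpoint uses only the treated subjects. Their starting value is the one on which they were selected. A value selected for showing a defect tends to look better on repeat testing whether or not the infusion did anything. Drift of the assay between screening and follow-up, and the natural course after diagnosis, enter the same difference and cannot be told apart from a drug effect.

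Placebo subjects carry all of these influences. Section 8.8 and Table 3 have them assayed at the same visits (Days 90, 150, 270, 360, 540 and 720). The information needed to remove the bias is therefore collected, but the criterion does not use it.

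At stake is whether a statement that AVT001 restored regulatory function can be attributed to AVT001. It is a secondary endpoint assessed in an exploratory manner, so no confirmatory claim hangs on it, but it is the trial's evidence on mechanism.

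**Working it through.** **The plan's own figures.** The current plan states no power or error rate for the potency criterion. Its one sample-size figure concerns adverse events and reproduces: 1 - 0.88^14 = 0.833, which meets the stated 80% or more.

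**Inputs from the documents.** 16 AVT001 and 8 placebo subjects (section 5.3); a defect found in nine of ten T1D subjects evaluated (section 5); two-sided 5% tests (SAP v2.0, section 7.3), which is 2.5% in the direction of recovery.

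**Assumptions, because the documents are silent.** A defect means low suppression on the scale later used at follow-up. Screening and follow-up values are bivariate normal with equal mean and variance and test-retest correlation r. The lowest fraction f of screening values is enrolled, and the screening value is the baseline. There is no drug effect, no drift and one follow-up visit. I take f = 0.90 from nine of ten, and r from 0.3 to 0.9.

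**Step 1: expected rise with no effect.** For a standard normal value kept only below its f-quantile z, the mean is -φ(z)/f. The follow-up mean is r times that. So the rise is (1 - r) × φ(z)/f SD. At f = 0.90, z = 1.282, φ(z) = 0.1755 and φ(z)/f = 0.195. The rise is 0.7 × 0.195 = 0.137 SD at r = 0.3 and 0.1 × 0.195 = 0.020 SD at r = 0.9.

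**Step 2: simulation at f = 0.90** (40,000 trials per row, no effect).

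| r | Mean rise (SD) | Paired test on 16 favours recovery | Single subject back above the cut-off | AVT001-versus-placebo test on change favours AVT001 |
|---|---|---|---|---|
| 0.3 | 0.138 | 6.4% | 8.7% | 2.4% |
| 0.5 | 0.099 | 5.6% | 7.5% | 2.5% |
| 0.7 | 0.058 | 4.8% | 5.9% | 2.5% |
| 0.9 | 0.020 | 3.6% | 3.4% | 2.4% |

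The paired test is an illustration; the plan prescribes none.

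**Step 3: sensitivity to selection.** Over the same r, the paired test favours recovery in 5.4-17.7% of trials at f = 0.75 and in 10.0-52.6% at f = 0.50. These values of f are not documented. They show only that the result depends on a quantity the documents withhold.

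**Step 4: the randomised comparison.** For every f (0.90, 0.75, 0.50, 0.25) and r tried, the between-arm test favours AVT001 in 2.4-2.6% of no-effect trials. Both arms were selected in the same way, so the regression cancels.

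**The case against.** The strongest reply is that section 9.8.1 describes an assay readout, hedges what it might suggest and hands the analysis to the SAP, while section 9.2 intends a comparison with placebo and section 9.8 offers an MMRM. So it would be wrong to say that the protocol never contemplates placebo for this endpoint. This stands as far as it goes. But sections 9.2 and 9.8 state intentions, and SAP v2.0 does not carry them out for potency. The between-arm Fisher test in the 2013 protocol is superseded and does not fill the gap.

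A reader might infer more than the documents support in four ways:

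- **That a no-effect trial would show recovery more often than not.** If any rise in the mean counted, it would do so in 57-69% of trials at f = 0.90. But section 9.8.1 does not say that any rise suffices, and it names healthy people as a reference. If function had to return above the defect cut-off, 3-9% of subjects would qualify.
- **That the best of six follow-up visits is set against one screening draw.** With no selection, a subject would then look improved with probability 6/7 = 0.857. But the text applies the same term, maximum suppression, to the period before treatment, where only one assay exists. A within-assay maximum is the natural reading.
- **That selection is strong because the defect must also be correctable.** Correctability is a separate response to co-culture. The documents do not say how it shifts the screening suppression value.
- **That the sponsor's separate report has no rule other than 9.8.1.** SAP section 3.3 gives no method for that report, so its content cannot be known from here.

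**Conclusion.** The point holds in a limited form. The stated criterion for regained function is uncontrolled, its baseline is the selecting value, and regression to the mean biases it towards recovery. The AVT001-versus-placebo comparison that section 9.2 intends is never specified.

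The size of the bias cannot be determined, because assay repeatability and the defect cut-off are not given. At the documented nine-of-ten share, with one follow-up visit and r from 0.3 to 0.9, the illustrative paired test fires upward in about 4-6% of trials against 2.5%. That is a modest inflation, and it grows if selection was stronger. It excludes assay drift and natural course, whose size and direction the documents do not give. The nine-of-ten share itself rests on ten subjects.

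This should be corrected. The endpoint's exploratory status and the hedged wording argue against a higher grade.

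**What to change.** SAP v2.0, section 4.4, foresees a further amendment before the final database lock. That amendment, and the sponsor's separate potency report, should state:

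- Reconstitution is judged by the AVT001-minus-placebo difference in maximum suppression at Day 150 (the protocol's primary time point), from a model adjusting for the screening value, with a 95% CI.
- Maximum suppression is the maximum within one visit's assay and is not taken across visits.
- Before-versus-after change within an arm and healthy-control values are descriptive and do not decide whether function was regained.
- The analysis is post hoc for data already unblinded. SAP v2.0, section 4.2, records unblinding on 17MAY2022, after the potency transfer, and delivery of the primary outputs on 10JUN2022. The Day 150 comparison can no longer be presented as prespecified.

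Section 9.8.1 should be reworded to match. No new samples are needed.

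The cost is precision. With equal SDs of change, the standard error goes from SD × √(1/16) = 0.250 SD for the treated arm alone to SD × √(1/16 + 1/8) = 0.433 SD for the difference. That is 0.433/0.250 = 1.73 times as wide, before any gain from adjusting for screening. The wider interval is what about 8 placebo subjects can support.

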### 9.8.2 C-Peptide AUC Calculation

The area under the stimulated C-peptide curve (AUC) over the first 4-hour period of a mixed meal glucose tolerance test will be conducted at baseline and Months 5, 12, 18, and 24. The AUC at each visit is computed using the trapezoidal rule that is a weighted sum of the C-peptide values over the 240 minutes. The weighted mean C-peptide is AUC/240 (pmol/mL). AUC values will then be log-

### **9.8.3 HbA1c, Antibodies**

Changes from baseline in HbA1c and antibodies will be tabulated.

## 10 Risks and Discomforts

The Investigator's Brochure is to be reviewed by the Investigator prior to initiation of this study. A brief summary of potential risks and discomforts is provided in this section. The drug handling manual includes additional detail as well as rescue medications that may be required.

### 10.1 Venipuncture

Subjects may experience slight discomfort at the site and rarely develop an ecchymosis or superficial thrombosis.

### 10.2 Leukapheresis

The most common adverse reactions from leukapheresis are paraesthesia, dizziness, mild chest tightness, or cough related to the reinfusion of autologous red blood cells treated with citrate and ecchymoses at the catheter sites.

Potential adverse reactions related to leukapheresis include:

- Exacerbation of symptoms from an underlying medical condition including migraine headache, asthma/emphysema, or cardiovascular disease.
- Infection at catheter sites
- Hypotension, hypertension, or bradycardia from citrate toxicity
- Allergic reactions
- Anemia, if red blood cells cannot be reinfused

### 10.3 Response to AVT001

The response to AVT001 would be to activate HLA-E restricted CD8+ T cells *in vivo*, which would in turn selectively down-regulate any anti-self responses to control autoimmune diseases. In pre-clinical animal toxicology studies, the data showed no adverse effect/reaction to the treatment. In general, DC-based therapies are considered safe and tolerable therapies, with less toxicity comparable to checkpoint inhibitors in use or in trial.

There might be infusion site reactions such as swelling and irritation after the treatment of AVT001. In addition, there may be risks/discomforts involved in this study that are not known at this time.

## 11 Safety and Adverse Events

The primary objective of this study is to assess the safety and tolerability of AVT001, as compared to placebo, in subjects with type 1 diabetes.

### 11.1 Definitions

#### 11.1.1 Unanticipated Problems Involving Risk to Subjects

Any incident, experience, or outcome that meets all of the following criteria:

- Unexpected in nature, severity, or frequency (i.e. not described in study-related documents such as the IRB-approved protocol or consent form, the investigators brochure, etc.)
- Related or possibly related to participation in the research (i.e. possibly related means there is a reasonable possibility that the incident experience, or outcome may have been caused by the procedures involved in the research)
- Suggests that the research places subjects or others at greater risk of harm (including physical, psychological, economic, or social harm).

#### 11.1.2 Adverse Event

Adverse event means any untoward medical occurrence associated with the use of a drug in humans, whether or not considered drug related. Adverse events may include safety findings considered to be clinically significant by the Investigator. An adverse drug event can therefore be any unfavorable and unintended sign (including an abnormal laboratory finding), symptom, or disease temporally associated with the use of a medicinal product, whether or not it is related to the medicinal product. Reporting an adverse event does not necessarily reflect a conclusion by the Investigator that the event is causally related to the drug.

AE is any symptom, sign, illness or experience that develops or worsens in severity during the course of the study. Intercurrent illnesses or injuries should be regarded as adverse events. Abnormal results of diagnostic procedures are considered to be adverse events if the abnormality:

- results in study withdrawal
- is associated with a serious adverse event
- is associated with clinical signs or symptoms
- leads to additional treatment or to further diagnostic tests
- is considered by the investigator to be of clinical significance

A preexisting condition is one that is present at the start of the study. A preexisting condition should be recorded as an adverse event if the frequency, intensity, or the character of the condition worsens during the study period.

Each adverse event in this study will be assessed for Grade, where Grade of an AE refers to the severity of the AE. Grade will be assessed according to CTCAE Version 4.03 or higher. The CTCAE displays Grades 1 through 5 with unique clinical descriptions of severity for each AE that are based on this general guideline, with higher grades indicating worse severity.

The relationship of any AE to study treatment will be assessed using the following definitions:

#### Definite (must have all 4)

- Has a reasonable temporal relationship to the intervention
- Could not have readily been produced by the subject's clinical state or have been due to environmental or other interventions
- Follows a known pattern of response to intervention
- Disappears or decreases with reduction in dose or cessation of intervention and recurs with re-exposure

**Probable (must have 3)**

- Has a reasonable temporal relationship to the intervention
- Could not have readily been produced by the subject's clinical state or have been due to environmental or other interventions
- Follows a known pattern of response to intervention
- Disappears or decreases with reduction in dose or cessation of intervention

**Possible (must have 2)**

- Has a reasonable temporal relationship to the intervention
- Could not have readily been produced by the subject's clinical state
- Could not readily have been due to environmental or other interventions
- Follows a known pattern of response to intervention

